valid and reliable measure of pain intensity [30]. The primary outcome of our study will be determined by the patient experience objectified with the NRS. The overall goal of this study is to improve the patient experience with cost-effective evidence-based treatment.

Research Plan and Design

Study Objectives

The primary objective is to determine the effectiveness of B&O suppositories in decreasing bladder injection pain at time of BoNT injection.

Our null hypothesis: Among patients given standard analgesia for BoNT treatment of overactive bladder (OAB), neurogenic detrusor overactivity (NDO), or refractory interstitial cystitis (IC), there is no difference in bladder injection pain scores with the addition of B&O suppository when compared to placebo suppository.

H₀: Mean Δ pain during procedure in active suppository group = mean Δ pain during procedure in placebo suppository group.

Change in pain (*Mean Δ pain*) is considered to be the difference in pain from the baseline pain level after analgesia, and after the first 10 injections.

Outcomes

The primary outcome will be bladder injection pain. Pain will be measured using numeric rating scales (NRS). Participants will score their preoperative baseline pain level when they check into the clinic for their procedure (P_o). Participants will report pain 40 minutes after administration of standard analgesia and suppository (just prior to bladder injection) (P_a). This will allow calibration of our primary outcome for patients with higher levels of baseline pain not related to the procedure (using themselves as controls). They will then be asked to rate bladder pain after the first 10 injections (midpoint of the procedure) intraoperatively (P_{10}). After the procedure is completed, which would be after 20 injections, the patient will again be asked to report their pain (P_{20}).

The operational definition of our primary outcome will be calculated difference in NRS pain score prior to procedure (P_a) and midway through procedure (P_{10}): Δ pain (intraoperative pain score – preoperative pain score).

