Secondary outcomes will include: pre-analgesia pain score (P_o), post-operative pain score (P_{20}), patient intolerance to the procedure, postoperative voiding trial results (pass/fail), and post void residual (PVR) results at 2 week follow-up (measured in ml, pass/fail), and diagnosis of urinary tract infection (accepted clinical definition of acute cystitis or a positive urine culture) at 2 week follow-up. PVRs < 200ml at 2 week follow-up will be considered passing result [31].

Participants will also rate their level of satisfaction with pain control immediately after the procedure using a simple Likert scale. This will be a 4-level scale ranging from 'not at all satisfied,' 'slightly satisfied,' 'mostly satisfied,' and 'very much satisfied.'

Expected Results

Investigators believe that participants randomized to the B&O suppository group will experience less bladder pain (average pain) during the BoNT injection procedure than those that were assigned to the placebo group.

Study Type and Design

This study is a randomized, pilot trial. Clinical investigators and participants will be blinded to the randomization groups. Participants, whom have elected to receive BoNT injection therapy, will be randomized to receive either a placebo or B&O suppository prior to the procedure. Pain will be assessed prior to the procedure, during the procedure, and after the procedure.

Sample size

Sample size is calculated assuming the group receiving the B&O suppository reports an average intra-procedural pain (P_{10}) score of 4.5, and assuming the control group (placebo) reports an average intra-procedural pain (P_{10}) score of 8. The assumed standard deviation is 3. Based on a power of 0.8, the required sample size per randomization group is 13. The total sample size required to achieve a power of 0.8 for this pilot trial would be 26 (13 per group).

Randomization

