Eligible participants will be assigned with equal probability to one of two treatment groups: belladonna and opiate (B&O) suppository and inactive placebo suppository. Block randomization will be utilized to maintain balance between study group sizes over time and to enhance blinding of the clinical investigators; a repeated run of placebo or active suppositories may lead to an anticipatory bias effect on subsequent participants. An online randomized block generator will be utilized. Block size will be randomized and will not be revealed to clinical investigators. As the proposed study is double-blinded, selection bias is unlikely.

Study drug suppositories will be randomized in sequential pill canisters. Aside from standard indications to do otherwise, treatment allocation will remain concealed until enrollment and follow-up visits have been completed.

Working with the compounding pharmacy, an unblinded data coordinator will label, and track, the active and placebo drug assignments. Once the patient has consented to participate in the study, the Principal Investigator will assign the participant sequentially, and will notify the data coordinator and compounding pharmacy. Based on a sequential numbering system, the participant will be randomized to receive either the B&O suppository or the inactive placebo suppository based on the block assignment. The Principal Investigator will complete an authentic prescription in order to comply with all Drug Enforcement Administration (DEA) requirements for securing Schedule 2

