narcotics. The prescription will be provided to the compounding pharmacy, which will fill the prescription based on the pre-determined randomization scheme. The compounding pharmacy will document and deliver the pill canister matching the participant's ID number, to the clinic and provide it to the Principal Investigator to store in a locked medicinal refrigerator in a locked room until the day of the procedure. Prior to administering the suppository to the patient during the procedure, the Principal Investigator will open the pill canister and document the pill canister number and the number labeled on the suppository in the patient's medical record, and study documents. If unveiling the randomization for a participant is required, the Principal Investigator can call the data coordinator or the compounding pharmacy, and the coordinator or the lead pharmacist will reveal the participant's randomization assignment over the phone. Monthly meetings will be conducted to audit the enrollment and to ensure randomization procedures are conducted appropriately.

Statistical Analysis

Preoperative demographic variables including age, race, parity, body mass index (kg/m^2), menopausal status, smoking status, medical comorbidities, and indication for BoNT treatment (OAB vs. NDO) will be compared between active and placebo patients. Continuous variables will be compared using Student t-tests. Categorical variables will be described as frequency data (proportions & percentages) and compared using Chi-square or Fisher's exact test (when expected values in any cell are less than 5). Ordinal variables will be compared using Wilcoxon Rank Sum tests.

An intent-to-treat analysis approach will be used. Results for the active group versus the control group will be compared with paired t-tests if the data are normally distributed and with Mann-Whitney tests if the data are skewed. Regression modeling will be used to analyze the relationship between our primary outcome with the following predictor variables; active vs. placebo, indication for BoNT injection (OAB vs. NDO), demographic variables, and pain scores (before-during-after procedure). Interactions between variables will be assessed and, if significant, included in the model.

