Confounding variables will be included in the model if point estimates change by more than 20% with their inclusion. Continuous variables will be assessed for linearity and converted to categorical variables as indicated by model fit statistics (c-statistic, Deviance, Pearson, Hosmer-Lemeshow). Cochran-Armitage and Goodness of Linear Fit tests will be used to evaluate for linear trends between suppository treatment and our primary outcome.

All statistical analyses will be two-sided. P-value of less than 0.05 is considered to be statistically significant. An interim analysis will be performed one year after Institutional Review Board if the study has not completed data collection within one year. Results will not be given to participants.

Participants

Patients will be approached for participation once they have selected BoNT therapy for treatment of overactive bladder (OAB), neurogenic detrusor overactivity (NDO), or refractory interstitial cystitis (IC).

To be included in this study, patients must be 18 years old or older at the time of the informed consent discussion, have met clinical criteria under outside care or during the Principal Investigator's routine standard of care for BoNT injection therapy (failed initial medical management), and there must be no contraindication to BoNT therapy as outlined by drug manufacturer guidelines (Table 1). Patients will have elected to have the BoNT injection therapy prior to being offer enrollment into the study for either OAB, NDO, or IC.

Patients will be excluded for pregnancy, currently nursing a baby, age less than 18 years, or anticipated geographic relocation within the first 3 months following treatment. Patients will be excluded if the patient reports an allergy to morphine, belladonna, or opiates. Patients will also be excluded if participating in another research study. Individuals unable to provide informed consent or to complete two-week follow-up bladder testing (post-void residual) or data collection will also be excluded. Prior to randomization, a data coordinator will verify eligibility and completeness of baseline data.

Participants will be withdrawn or terminated from participating in the study by a clinical investigator if they fail to undergo the BoNT injection procedure and do not reschedule before the conclusion of the study.

[figure not shown]

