Assemble project staff, create study protocol, submit for IRB approval and study funding													
Submit project for IRB approval and funding													
Receive IRB Approval			X										
Train study team and support staff													
Recruit patients from local providers offices													
Enroll patients and collect data													
Team meetings to discuss research plan, data quality, and progress on objectives													
Conduct preliminary analysis													
Review findings with team													
IRB Continuing Review													
	Academic Year 2016 - 2017												
Finalize data analysis and conclusions													
Draft abstract and submit to regional/national conferences		X											
Disseminate preliminary findings at regional/national conferences				X						X			
Draft manuscript													
Submit manuscript for publication							X						

Budget and Justification

Investigators will be requesting funding to cover costs related to the study and registration for the Principal Investigator and the Resident Investigator to present the findings of this study at the 2016 American Urogynecologic Society Annual Meeting. A detailed budget is provided below.

Personnel Costs: **\$0.00**
[name], MD, Principal Investigator (PI), will be responsible for managing and providing direction on all aspects of the project, ensuring that the budget and timetable targets are met, and providing direction to the other research personnel. Specifically he will facilitate communication between members of study team, and oversee conduct of the study, ensure all requirements for the Institutional Review Board are met, and contribute to reports, and dissemination. [name] will be performing the clinical procedures associated with this study, perform the data analysis and create reports, and disseminate results at national meetings.

[name], PGY-3, Co-investigator, will be responsible for managing and providing direction on all aspects of the project, ensuring that the budget and timetable targets are met, support Institutional Review Board approval/revisions, and providing direction to the other research personnel. Specifically she will facilitate communication between members of study team, and oversee conduct of the study personnel, perform study procedures, assist with data analysis, and create reports, and dissemination at national meetings.

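### No analysis of the primary hypothesis is named as decisive, so the 5% error rate is not guaranteed: it is about 5% to 10%, depending on which route is claimed

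*Combined protocol and SAP*

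**What the plan says.** Study Objectives gives a single null: "Mean Δ pain during procedure in active suppository group = mean Δ pain during procedure in placebo suppository group". Outcomes defines Δ pain as P10 (after 10 injections) minus Pa. Pa is scored 40 minutes after the suppository, whereas P_o is scored at check-in, before any analgesia.

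Statistical Analysis then gives three ways to relate treatment to that outcome:

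1. A group comparison "with paired t-tests if the data are normally distributed and with Mann-Whitney tests if the data are skewed". No normality criterion is stated.
2. A regression: "Regression modeling will be used to analyze the relationship between our primary outcome with the following predictor variables". The list holds treatment arm, indication, demographics and pain scores from before, during and after the procedure. Interactions stay if significant. Confounders stay if they move point estimates by more than 20%.
3. Cochran-Armitage and goodness-of-linear-fit tests for trend between suppository and primary outcome.

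The level is common to all: "All statistical analyses will be two-sided", and "P-value of less than 0.05 is considered to be statistically significant". There is no hierarchy or adjustment, and no route is labelled primary or supportive.

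On blinding, Randomization says "treatment allocation will remain concealed until enrollment and follow-up visits have been completed". Budget and Justification says that the Principal Investigator "will be performing the clinical procedures associated with this study, perform the data analysis and create reports".

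**The concern.** One hypothesis with several p-values and no deciding rule leaves the meaning of a positive trial open. If Mann-Whitney gave p=0.07 and the regression p=0.04, nothing in the plan says whether the null is rejected. With 26 patients, a result near 0.05 could turn on which analysis is reported.

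Two features go beyond missing detail. The covariate and interaction rules let the data shape the treatment estimate. The predictor list also includes the pieces from which the outcome is built, so the analyst would have to improvise the model. If the rank test is selected, the group comparison gives no estimate for a null that is written in means.

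**Working it through.** **The plan's own figure.** Sample size gives means of 4.5 and 8 (difference 3.5), SD 3 and power 0.8. The two-sided 0.05 level comes from Statistical Analysis. By the normal formula, n = 2 × (1.96 + 0.84)² × 3² / 3.5² = 11.5, so 12 per group. The two-sample t calculation gives 12.57, so 13, with power 0.814 at 13. This agrees with "Based on a power of 0.8, the required sample size per randomization group is 13".

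**Error rate under the null.** The simulation ran 10,000 trials per scenario, 13 per arm, with a Monte Carlo standard error of about 0.2-0.3 points. The following are assumptions, not in the documents:
- The outcome is P10 minus Pa from normal scores, the same from scores rounded and bounded to 0-10 (NRS), or an exponential (skewed) outcome.
- The Pa-P10 correlation is 0.5 in the first two scenarios.
- The t-test is read as unpaired, and Shapiro-Wilk at 0.05 chooses between it and Mann-Whitney.
- Six null covariates plus Pa are screened by the 20% rule.
- The trend test runs over outcome quartiles.

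| Analysis that decides | Normal | NRS | Skewed |
|---|---|---|---|
| Unpaired t-test only | 5.2% | 5.2% | 4.2% |
| Mann-Whitney only | 4.5% | 4.9% | 4.2% |
| Test chosen by normality check | 5.3% | 5.3% | 5.1% |
| Regression, all covariates fixed in advance | 5.4% | 5.1% | 4.7% |
| Regression, 20% rule | 6.3% | 7.6% | 6.7% |
| Chosen test or 20%-rule regression | 8.4% | 8.2% | 8.5% |
| The same, or trend test | 9.2% | 9.8% | 9.1% |

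The normality-driven switch costs almost nothing. The regression is also sound when its covariates are fixed in advance, so the rise to 6.3-7.6% comes from the selection rule. The routes are strongly correlated, so the rates stay below the 1 − 0.95³ = 14.3% of three independent tests.

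A second run of 8,000 null trials, also on rounded 0-10 scores with six null covariates, gave 5.5% for the group rule, 7.5% for the regression and 8.2% for either. The two disagreed on significance in 3.4% of trials. A further run gave 6.8% for the 20%-rule regression, against 4.9% for one prespecified model with P_o.

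**Interactions.** With six null covariates, at least one treatment-by-covariate interaction fell below 0.05 in 26-27% of null trials (1 − 0.95⁶ = 26.5%). Once such a term enters, the treatment coefficient is no longer the overall difference between arms. The table does not include this step or the interim analysis.

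**The predictor list.** If Pa and P10 both enter a linear model for P10 − Pa, then

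P10 − Pa = (1 × P10) + (−1 × Pa) + (0 × treatment)

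The fit is exact, and nothing is left for treatment to explain. P20 is scored after treatment, so adjusting for it can remove part of the effect under study. The c-statistic and Hosmer-Lemeshow test presuppose a binary outcome and Cochran-Armitage a binary variable, so the type of regression for a numeric change score is not settled either.

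**The case against.** The strongest reply is that the plan never says success may be claimed on any route. The group comparison reads naturally as the test of active against control. The regression has a different stated purpose, which is to describe relationships with several predictors. On that reading the error is 5.1-5.3% and there is no inflation. The trial is also a 26-patient pilot with one primary outcome and one null. All of this stands as a possible reading, but the plan does not state it. The same p<0.05 rule covers every analysis, and a trial with a formal null and 80% power needs a stated deciding test.

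Some stronger readings are tempting but not supported:

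- **The error rate exceeds 5%.** This holds only if the regression decides or any route may be claimed. The documents leave that open.
- **Choosing the test from the data inflates error.** The table shows that it does not, to any practical extent.
- **Mann-Whitney would almost always be used.** A mean of 8 with SD 3 on an assumed 0-10 scale implies a strong ceiling, and a normality check on P10 alone sends about 97% of simulated trials to Mann-Whitney. The primary outcome is P10 minus Pa, however. For that difference the share was about 15-65% over a range of assumed Pa values, and about 15% in a separate null run.
- **Trend tests push the error to 11.5%.** That figure needs a median split, which the plan does not mention. An uncorrected test on such a split with 13 per arm is anti-conservative by itself.
- **Choices are made with arms visible.** The plan says when concealment ends, not when analysis choices are fixed. A normality check needs no arm labels, and other personnel assist with the analysis. The 20% rule and treatment interactions do need the treatment term, and no data lock is described. The plan thus permits unblinded choices but does not say they will occur.

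**Conclusion.** The concern holds in limited form. The primary null has three analysis routes at two-sided 0.05 and no decisive one, so 5% is not guaranteed. The error is about 5% if the group test decides, about 6-8% if the regression with the 20% rule decides, and about 8-10% if any route may carry the claim. These figures rest on simulated null data with assumed covariates, correlations, normality rule and trend categories.

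Two parts do not depend on the simulation. Mann-Whitney does not estimate the mean difference in the stated null, and the listed pain predictors either reproduce the outcome exactly or adjust for a post-treatment score. This should be fixed before analysis. It does not undermine the design or the sample size.

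**What to change.** In Statistical Analysis, name one decisive primary analysis: an unpaired comparison of P10 minus Pa by a linear model on treatment, with P_o as the only covariate. Report the adjusted mean difference with its 95% CI and state that this result alone decides the null. P_o suits the purpose because it is already collected and precedes the suppository, whereas Pa follows it.

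Remove the 20% rule and the during- and after-procedure pain scores from that model. Label Mann-Whitney, other regressions and the trend tests as supportive. In Randomization, keep the allocation closed until the dataset and analysis script are locked.

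The cost is a paragraph of wording and a later code break. The planned 13 per group and all patient procedures stay as they are. The downside is that a favourable p-value from a supportive analysis can no longer carry the conclusion. A permutation p-value, or a bar on significance claims for secondary outcomes, would be reasonable but is a matter of preference and is not needed to close this gap.

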If the study subject were to be injured as a result of study procedures (separate from the BoNT therapy), subjects will be advised to immediately contact the Principal Investigator, [name] [REDACTED] [name] will decide what type of treatment, if any, is best for the study participant at that time.

Data Collection and Protection

Data Collection Procedures

Data collection will occur after obtaining informed consent for the patient to participate in the study. Demographic data will be collected to include clinical, surgical, functional, post-procedure, charted data collected as part of routine clinical visit and standard of care (Table 4). Data will be collected on a paper form (Appendix B – Data Collection Form). Follow-up data will include newly charted clinical and functional data.

Table 4. Summary of Participant Demographic Data Collected
Date of 1st consultation
Height
Weight
Body Mass Index
Race/Ethnicity
Smoking status
Menopausal status
Diagnoses
Prior surgeries
Past medical history
Medications
Indication for BoNT injection procedure

The day of the procedure, the participant will check in at the front desk. A nurse will escort the participant back to the procedure room for preparation. The participant will be given a pain assessment form with a numeric rating scale that will ask the participant to evaluate their bladder pain prior to standard analgesia and the procedure (Appendix C – Pain Assessment Form - Po). After completing the assessment, the participant will be positioned for the procedure and will be administered standard analgesia plus active or placebo suppository (based on randomization assignment).

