Aside from suppository placement, BoNT injection protocols that are in compliance with best practices established by Allergan® and the FDA will be followed. In summary, BoNT will be reconstituted in 10ml normal saline and injected in 1/2ml increments (20 injections). Standard analgesia consists of bladder instillation with 50-60ml of 1% lidocaine solution with 10ml of sodium bicarbonate. Instillation is maintained for 40 minutes prior to the procedure. During that time, the patient will rotate while on procedure table (10 minutes on supine, 10 minutes prone, 10 on each side) to maximize bladder wall contact with anesthetic. The patient will then be placed in lithotomy position for cystoscopic injection of BoNT. A 17 french 30 degree cystoscope will be used. Injection will be carried out using a flexible botox injection needle designed for the procedure. All patients will undergo standard screening for preoperative UTI and antibiotic prophylaxis per accepted guidelines.

After 40 minutes of receiving the analgesic and suppository, and right before the procedure, the participant will be asked to report their bladder pain using a numeric rating scale (Appendix D – Pain Assessment Form – Pa-P20).

Patients will undergo 20 total injections at time of BoNT treatment. An investigator will perform pain assessments during the procedure. During the procedure, the participant will be asked their bladder pain using the numeric rating scale after the first 10 of 20 injections performed during the procedure and after the next 10 of 20 performed during the procedure (Appendix D – Pain Assessment Form – Pa-P20).

After the procedure is completed, the participant will be asked to complete a voiding trial, and will be given a pain assessment form, answering a Likert scale question regarding their satisfaction with their pain management during the procedure (Appendix E – Pain Assessment Form - Post BoNT). After the voiding trial is completed and the Principal Investigator has provided standard medical counseling and care after the procedure, the participant is released from the clinic.

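### The regression of P10 minus Pa lists during- and after-procedure pain as predictors; in a linear model with the scores entered together, its treatment coefficient is zero (if *before* is Pa) or distorted, usually toward zero (if *before* is Po)

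*Combined protocol and SAP*

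**What the plan says.** All references are to the Combined protocol and SAP.

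- Outcomes section, primary outcome: "The operational definition of our primary outcome will be calculated difference in NRS pain score prior to procedure (P_a) and midway through procedure", that is, P10 minus Pa.
- Statistical Analysis section: this outcome is regressed on a list of predictors, "active vs. placebo, indication for BoNT injection (OAB vs. NDO), demographic variables, and pain scores (before-during-after procedure".
- The *during* and *after* scores are P10 and P20. Data Collection Procedures has pain asked "after the first 10 of 20 injections performed during the procedure and after the next 10 of 20 performed during the procedure". The secondary outcomes include the "post-operative pain score (P_{20}), patient intolerance to the procedure".
- The *before* score is not named, and two scores fit. Pa is the one the primary outcome uses as its pre-procedure value, but it follows dosing: "Participants will report pain 40 minutes after administration of standard analgesia and suppository (just prior to bladder injection". Po is taken at check-in: "Participants will score their preoperative baseline pain level when they check into the clinic for their procedure". Its form asks patients to "evaluate their bladder pain prior to standard analgesia and the procedure".
- A separate between-group test is also planned: "Results for the active group versus the control group will be compared with paired t-tests if the data are normally distributed", with a rank test for skewed data.

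No section removes P10 or P20 from the regression. The 20% change-in-estimate rule and the short paragraph on confounding (before Standard of Care Procedures) do not exclude them.

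**The concern.** A treatment effect on P10 minus Pa cannot be estimated while P10 is held fixed, because P10 is where most of the effect is expected to appear. P20 is also measured after treatment and is expected to carry the same effect, so adjusting for it can remove or distort part of what the trial is looking for.

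This regression is the plan's only adjusted treatment estimate. In a 26-patient pilot, a clear unadjusted difference followed by an adjusted coefficient near zero could be read as an effect that vanishes on adjustment, when the model itself produced that result.

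**Working it through.** **Inputs from the plan.** Sample size section: mean P10 of 4.5 (active) and 8 (placebo), so an effect of 4.5 - 8 = -3.5; SD 3; power 0.8; 13 per group. Statistical Analysis section: two-sided 0.05.

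**Assumed, because the documents give no figures.** Effect on P20 also -3.5; no effect on Po; SD 3 for every score; all within-arm correlations equal to r = 0.3 / 0.5 / 0.7; effect on Pa either 0 or -1.

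**1. The plan's own figure.** A two-sample t-test for a difference of 3.5 with SD 3 needs n = 12.57, so 13 per group and 26 in total. Power at 13 is 0.814. The stated sample size is reproduced. The change score has SD 3 x sqrt(2(1 - r)) = 3.55 / 3.00 / 2.32. The unadjusted t-test on it has simulated power of about 0.68 / 0.82 / 0.95 (good to about 0.01; at r = 0.5 the exact value is the 0.814 above).

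**2. *Before* is Pa.** P10 - Pa = 1 x P10 - 1 x Pa + 0 x P20 + 0 x arm. The residual is zero, R-squared is 1 and the arm coefficient is 0. Simulated 26-patient fits gave at most 2e-13 in absolute value, which is rounding error. No assumed correlation is involved.

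**3. *Before* is Po.** With P10 in the model, the P10 part of the outcome is fitted exactly. What remains is minus the regression of Pa on arm, Po, P10 and P20. So

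arm coefficient = b10 x (effect on P10) + b20 x (effect on P20) - (effect on Pa),

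where b10 and b20 are the within-arm slopes of Pa on P10 and P20, with Po also in the model. Under equal correlations both are b = r/(1 + 2r), and the coefficient is -7b - (effect on Pa).

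| | r = 0.3 | r = 0.5 | r = 0.7 |
|---|---|---|---|
| b | 0.1875 | 0.25 | 0.2917 |
| Coefficient, Pa unshifted (true -3.5) | -1.31 | -1.75 | -2.04 |
| Power, this model | 0.14 | 0.26 | 0.43 |
| Power, unadjusted | 0.68 | 0.82 | 0.95 |
| Coefficient, Pa lowered by 1 (true -2.5) | -0.31 | -0.75 | -1.04 |
| Wrong sign, this model, Pa lowered by 1 | 42% | 28% | 17% |
| Wrong sign, unadjusted, Pa lowered by 1 | 4% | 2% | 0.3% |

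Powers and wrong-sign rates are from simulated trials of 26.

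**4. Less uniform correlations.** Let Po-Pa be 0.6, P10-P20 be 0.7 and the other four 0.3. Then bPo + 0.6b = 0.6 and 0.3bPo + 1.7b = 0.3, so 1.52b = 0.12 and b = 0.0789. The coefficient is -7 x 0.0789 = -0.55 with Pa unshifted, and +0.45 with Pa lowered by 1. Over 20,000 draws of assumed correlations, SDs and effects, the coefficient was smaller in absolute size than the true effect in 97%. That share depends on the ranges drawn.

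**5. P20 entered without P10.** With Po and P20 entered, the coefficient is -3.5 - g x (-3.5), where g is the within-arm slope of P10 - Pa on P20.

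- All correlations equal: g = 0, coefficient -3.5 (no bias).
- P20-Pa 0.6, P20-P10 0.4, others 0.5: g = -0.2/0.75 = -0.267, coefficient -4.43.
- P20 correlated 0.5 with both, Po-Pa 0.7, Po-P10 0.3, others 0.5: g = (0.5 x 0.4)/0.75 = 0.267, coefficient -2.57.

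So P20 alone can bias the estimate in either direction, or not at all.

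**6. Bounded scores.** With scores rounded and cut to 0-10 (assumed placebo means Po 3, Pa 2, P10 and P20 8), the model with Po, P10 and P20 gives -0.95 / -1.22 / -1.31 against -3.0 unadjusted.

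**7. If a logistic model were meant.** Some of the listed fit statistics suggest one. A dichotomised P10 - Pa is fully determined by P10 and Pa, so with both entered the model is separated and gives no usable treatment estimate.

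**The case against.** **The plan does not say that all scores enter one linear model.** True. It says only that regression will be used, and it describes selective inclusion of confounders. The exact zero therefore holds for a linear model with Pa and P10 entered together. Treating P10 as a candidate does not rescue the plan: adding P10 to an arm-only model moves the large-sample coefficient from -3.5 to -3.5r = -1.05 / -1.75 / -2.45, a change of 70% / 50% / 30%. Each exceeds 20%, so the rule would tend to keep it.

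**An analyst would notice.** Largely true if *before* is Pa, since R-squared is 1. If *before* is Po, the model fits without error, but it would be too strong to say that nothing would show: P10 is itself significant in about 88-93% of simulated trials, so a component of the outcome would stand out as its dominant predictor. That is a cue to a careful reader and does not correct the treatment estimate.

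**The sizes rest on assumptions.** They do. Equal correlations are a convenience, and other choices give values nearer zero or of opposite sign. The identity and the misuse of P10 as a predictor do not depend on them.

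**It is only a supplementary model.** This stands and limits the point. A reader might infer that the trial's main comparison is invalid or that 26 patients are too few because of this. The documents do not support that: the group comparison is specified separately and contains no pain-score covariates (its paired wording is another matter), and the sample size is reproduced.

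**Conclusion.** The regression is wrong as written and should be corrected, but the fault stops there. In a linear model with the scores entered together, the treatment coefficient is exactly 0 if *before* is Pa. If *before* is Po it is distorted, usually toward zero: -1.31 to -2.04 for a true -3.5 under equal correlations of 0.3 to 0.7, and -0.55 under one less uniform pattern.

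A reader might infer that the adjusted analysis will show the suppository making pain worse. The documents do not support that: a reversed expected sign needs an effect of the suppository on Pa, for which they give no figure, together with unfavourable correlations. The wrong-sign rates are illustrative. Nor can one say that P20 alone always biases the estimate, or in which direction.

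Confidence is high in the identity and in the need to remove P10 and P20; it is lower for any particular size. The missing interstitial cystitis category and the fit statistics meant for binary outcomes are separate points and carry no weight here.

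**What to change.** In the Statistical Analysis section:

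- remove P10 and P20 from the predictors, and analyse P20 only as an outcome;
- state that the *before* covariate is the check-in score Po, the only pain score taken before the suppository;
- limit candidates for the 20% rule to variables recorded before the suppository.

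A model adjusting for Pa may be shown as a labelled sensitivity analysis. It should not replace the Po model, because Pa is scored 40 minutes after dosing. If the suppository lowers Pa by 1, the Pa-adjusted coefficient is -2.5 + (r - 1) = -3.2 / -3.0 / -2.8 instead of -2.5, whereas adjusting for Po returns -2.5.

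The cost is wording: the primary outcome is unchanged and Po is already collected. Po may add little precision. Under equal correlations it alone costs about 0 to 2 points of power against the unadjusted test. If a three-level indication term is also kept and is not prognostic (assumed 70/20/10 split), the total cost is about 3 to 7 points.
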